2.1.4.2 Adverse events variables

Adverse event observation period

- Pretreatment adverse events are AEs that developed or worsened or became serious from the signed informed consent date up to first administration of double-blind IMP.
- Treatment-emergent adverse events (TEAEs) are AEs that developed or worsened or became serious during the TEAE period.
- Posttreatment adverse events are AEs that developed or worsened or became serious during the posttreatment period.

All AEs (including SAE, AESI and EOSI) will be coded to a LLT, PT, HLT, HLGT, and associated primary SOC using the version of MedDRA currently in effect at Covance at the time of database lock.

The occurrence of AEs (including SAE, AESI and EOSI) will be recorded from the time of signed informed consent until the end of the study (see [Section 2.1.4](#)) or the resolution/stabilization of all SAE, AESI and EOSI.

AESI include:

- Pregnancy.
- Symptomatic overdose with IMP/NIMP.
- Alanine aminotransferase (ALT) increase >3 times upper limit of normal (ULN).

EOSI include:

- Major adverse cardiovascular events (MACE [cardiovascular death, myocardial infarction, or stroke]) and other specific CV events (eg, heart failure requiring hospitalization).
- Severe hypoglycemia.
- Genital mycotic infections (to include vulvovaginal candidiasis in females and candida balanitis in males).
- Urinary tract infections (UTIs).
- Clinically relevant volume depletion and events related/possibly related to volume depletion.
- Diarrhea.
- Pancreatitis.
- Bone fractures.
- Venous thrombotic events (VTEs) to include deep venous thrombosis and thromboembolism (to include pulmonary embolism).
- Diabetic ketoacidosis (DKA).
- Renal events, to include 50% decline in eGFR, end stage kidney disease, renal death.
- Malignancies of special interest (breast, bladder, renal cell, Leydig cell, pancreatic, prostate, and thyroid cancer).
- Adverse events leading to an amputation.

The Clinical Endpoint Committees (CECs) will, in a blinded manner, review and adjudicate all deaths, MACE/selected CV events (myocardial infarction, stroke, unstable angina requiring hospitalization, and heart failure requiring hospitalization), selected renal events, bone fracture, and DKA.

Two independent committees will review safety events that require ongoing monitoring in case a safety signal is identified. These events are: 1) potential cases of drug-induced liver injury

(DILI), and 2) cases of amputations. The two committees will review the cases in a treatment-blinded manner and will present their assessments to the Data Monitoring Committee (DMC).

AESI and EOSI will be identified based on criteria in [Table 3](#).

Table 3 - Criteria for AESI and EOSI

AE Grouping	Criteria
AESI	
Pregnancy	e-CRF "Pregnancy".
Symptomatic overdose with IMP/NIMP	"Overdose of Tablet", "Overdose of Capsule" or "Overdose of NIMP" checked and "Symptomatic overdose" checked in e-CRF "Overdose".
Alanine aminotransferase (ALT) increase >3X upper limit of normal (ULN)	e-CRF "ALT increase".
EOSI adjudicated	
Cardiovascular death	Positively adjudicated by CEC: "Cardiovascular" or "Undetermined" as the primary cause of death.
Myocardial infarction, unstable angina requiring hospitalization	Positively adjudicated by CEC: Yes to the question "Does the event meet the definition of an MI for this study?", or Yes to the question "If event is not an MI, does the event meet the definition of an UA Requiring admission to hospital or emergency room, for this study?"
Stroke	Positively adjudicated by CEC: Yes to the question "Does the event meet the definition of a Stroke for this study?"
Heart failure requiring hospitalization	Positively adjudicated by CEC: Yes to the question "Does the event meet the definition of a Heart Failure Event for this study?"
Bone fractures	Positively adjudicated by CEC: Yes to the question "Did the Fracture occur?"
Diabetic ketoacidosis	Positively adjudicated by CEC: Yes to the question "Does this event meet the criteria to be a DKA event?"
EOSI Renal events where select events adjudicated	
Sustained ≥50% decrease in eGFR	
 For ≥50% decrease in eGFR from baseline, 
 Confirmed ≥50% decrease in GFR for ≥30 days with no reversible cause as recorded in e-CRF "eGFR decrease", OR Positively adjudicated by CEC: Yes to the question "Does the subject meet the criteria of CKD progression" for ≥50% decrease in eGFR.
Sustained eGFR <15 mL/m ² /1.73 m ²	
 For eGFR <15 mL/m²/1.73 m², 
 Confirmed eGFR <15 mL/m²/1.73 m² for ≥30 days with no reversible cause as recorded in e-CRF "eGFR decrease", OR Positively adjudicated by CEC: Yes to the question "Does the subject meet the criteria of CKD progression".

Statistical Analysis Plan

Version:3

Lexicon Pharmaceuticals, inc. Protocol No. EFC14838

^b AE potentially leading to an amputation not belong to the EOSI list defined in protocol the item is included and analyzed due to its relevance in regards to lower limb complications and amputations

2.1.4.3 Deaths

The deaths observation period are per the observation periods defined above.

- Death on-study: deaths occurring during the on-study observation period.
- Death on-treatment: deaths occurring during the TEAE period.
- Death poststudy: deaths occurring after the end of the study.

2.1.4.4 Laboratory safety variables

The clinical laboratory data consist of blood analysis (including hematology, clinical chemistry, amylase, lipase and lipid profile) and urinalysis. Clinical laboratory values will be summarized in both standard international units and conventional units when applicable.

Blood samples for clinical laboratories will be collected at designated visits (see study flowchart in Appendix E). The following laboratory data will be measured at a central laboratory:

- Hematology
 - **Red blood cells and platelets:** hemoglobin, hematocrit, red blood cell, platelets count,
 - **White blood cells:** white blood cell, neutrophils, lymphocytes, monocytes, basophils, eosinophils.

- Clinical chemistry
 - **Metabolism:** glucose (serum), creatine phosphokinase (CPK),
 - **Electrolytes and minerals:** sodium, potassium, chloride, bicarbonate (ie, carbon dioxide), calcium, phosphorus, magnesium,
 - **Renal function:** blood urea nitrogen (BUN), creatinine, uric acid,
 - **Liver function:** total protein, albumin, ALT, aspartate aminotransferase (AST), alkaline phosphatase (ALP), total bilirubin, Lactic acid dehydrogenase (LDH).
- Lipid parameters (fasting): total cholesterol (TC), high density lipoprotein cholesterol (HDL-C), low density lipoprotein cholesterol (LDL-C) (calculated by Friedwald equation, see [Section 2.5.1](#)), Non-HDL-C (calculated as the difference between TC and HDL-C), triglycerides (TG).
- Pancreatic enzymes: lipase, amylase.

Urine samples will be collected at designated visits (see study flowchart in Appendix E). The central urinalysis includes:

- Urine dipstick includes: specific gravity, pH, protein, blood, ketones, bilirubin, urobilinogen, nitrite, and leukocyte esterase.
- Urine microscopy includes, but is not limited to: detection of formed cellular elements, casts, bacteria, yeast, parasites, and crystals in centrifuged urine sediment.

For creatinine and calculated eGFR, potentially clinically significant abnormality (PCSA) summaries will be presented in the safety section while descriptive summaries in the efficacy section.

Technical formulas are described in [Section 2.5.1](#).

2.1.4.5 Vital signs variables

Vital signs include: heart rate (HR), sitting systolic and diastolic blood pressure (SBP and DBP), temperature, and respiratory rate (see study flowchart in Appendix E for designated visits). They will be performed after the patient has been seated for at least five minutes. Blood pressure (BP) and HR will be assessed three times with at least one minute between each measurement following the 5-minute rest period, and prior to phlebotomy. The mean of the three measurements will be analyzed for each vital sign variable (HR, SBP, and DBP).

2.1.4.6 Physical examination

A complete physical exam will be performed at Visit 1 (Screening) Visit 10 (Week 26) and Visit 12 (Week 52). “Normal”, “Abnormal” or “Not done” as determined by the Investigator will be reported in the e-CRF by body system.

2.1.4.7 Electrocardiogram variables

The 12-lead ECGs will be performed at Visit 1 (Screening), Visit 10 (Week 26) and Visit 12 (Week 52). ECG status of “normal” or “abnormal” will be reported in the e-CRF as determined by the investigator.

2.1.5 Quality-of-life endpoints

The PQAT includes a 7-point Likert Scale for the patient to evaluate his/her subjective response to the treatment (-3 to +3 including 0 for a neutral response) and two free-text response questions to describe key advantages and disadvantages.

The PQAT will be administered to English-speaking patients at sites in English-speaking countries.

The patients will be asked to complete it electronically from home just before the on-site visits planned at Weeks 26 (Visit 10) and 52 (Visit 12). They will be asked to do it by themselves without any help from friends or relatives.

At the beginning of the Weeks 26 (Visit 10) and 52 (Visit 12) patient visits, Investigators will have to review patient answers (accessible on a web platform) in order to identify any potential AEs reported by patients within the open-ended questions.

All patients' answers will be analyzed qualitatively and quantitatively, as relevant, using appropriate data analysis software.

The analysis method for this exploratory analysis will be provided in a separate SAP and the analyses results will be documented in a separate report.

If a patient discontinues treatment with IMP during the Treatment Period, the patient will be asked to complete this qualitative assessment of treatment at time of discontinuation.

2.2 DISPOSITION OF PATIENTS

This section describes patient disposition for both patient study status and the patient analysis populations.

Screened patients are defined as all patients who signed the informed consent.

Randomized patients consist of all patients with a signed informed consent form who have had a treatment kit number allocated and recorded in the IRT database, regardless of whether the treatment kit was used or not.

For patient study status, the total number of patients in each of the following categories will be presented in the clinical study report (CSR) using a flowchart diagram or summary table:

- Screened patients.
- Run-in patients: patients who had a run-in record in IRT.

- Screen failure patients (including failures during run-in) and reasons for screen failure (see [Appendix A](#) for details on the mapping of inclusion and exclusion criteria under the original protocol and Amendment).
- Nonrandomized but treated patients.
- Randomized patients.
- Randomized but not treated patients.
- Randomized and treated patients.
- Patients who have completed the 52-week double-blind Treatment Period as scheduled.
- Patients who did not complete the 52-week double-blind Treatment Period as scheduled and the reasons for permanent treatment discontinuation.
- Patients who have completed the study as scheduled.
- Patients who did not complete the study as scheduled and the reasons for study discontinuation.
- Patients' end of study status (completed, not completed) and corresponding end of treatment status (completed, not completed).
- Status at last study contact.

For screened, run-in, screen failure, and nonrandomized but treated patients, percentages will be calculated using the number of screened patients as the denominator. All other categories of patients will be presented by treatment group and the percentages will be calculated using the number of randomized patients within each treatment group as the denominator. Reasons for treatment discontinuation will be supplied in tables giving numbers and percentages by treatment group. Patients prematurely discontinued from treatment and/or study, along with reasons for discontinuation, will also be listed.

A summary of the distribution of patients by country and center will also be provided (overall number of patients screened, run-in, randomized, and treated, as well as number of patients randomized, discontinued from study treatment, and discontinued from study for each treatment group).

Patients treated but not randomized, patients randomized but not treated and patients randomized but not treated as randomized will be identified and described in separate listings. The patients of the third category (randomized and not treated as randomized) will be part of efficacy and safety analyses (see [Section 2.3](#)). Patients randomized but not treated will be included in efficacy analysis. Safety data of patients treated but not randomized will be reported separately.

The randomization strata (HbA1c at Screening [$\leq 8.5\%$, $>8.5\%$] and SBP at Screening [<130 , ≥ 130 mmHg]) assigned by IRT will be summarized. The percentages will be calculated using the number of randomized patients as the denominator. The discrepancy between the strata assigned by IRT and the information reported on e-CRF will be listed for all randomized patients.

Kaplan-Meier (KM) plots of the cumulative incidence of double-blind IMP discontinuations due to any reason and due to AEs will be provided for the double-blind Treatment Period separately

(see [Section 2.5.4](#)). A listing of these patients, along with the reason for discontinuation of treatment, study completion status and the reason for discontinuation of study, will be provided.

All important deviations including randomization and drug-dispensing irregularities will be summarized in tables giving numbers and percentages of deviations by randomized treatment group.

Additionally, the analysis populations for safety and efficacy defined in [Section 2.3](#) will be summarized in a table by number of patients in the randomized population.

- Efficacy population: ITT population.
- Safety population.

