- Initiate an evaluation and treatment of intercurrent disease (to be reported in AE/concomitant medication parts of the e-CRF and the medical record).
- Stress on the absolute need to be compliant with treatment.

- Organize a specific interview with the patient and a Registered Dietician or other qualified nutrition professional and to reinforce on the absolute need to be compliant to diet and lifestyle recommendations, and schedule a FPG/HbA1c assessment at the next visit (in case the next visit is a phone call, it should be replaced by an on-site visit).
- If patient is still in the first 18 weeks of the study and glimepiride is not uptitrated to the maximum dose evaluate if uptitration of glimepiride is possible.

If none of the above mentioned reasons can be found, or if appropriate action fails to decrease FPG/HbA1c under the threshold values, rescue medication may be introduced.

- Rescue medication can be added up to the Investigator's decision except for SGLT2 inhibitors, and sulfonylurea.
- The patient continues the study treatment (blinded) and stays in the study in order to collect efficacy and safety information. The planned visits and assessments should occur until the last scheduled visit.
- Rescue therapy is considered a NIMP. Rescue therapy is to be reported in the e-CRF. This information should include specific drug name, dose, route of administration, and frequency.

If not covered by health insurance, the cost of rescue therapy will be reimbursed where permitted by local regulations.

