1.3 DETERMINATION OF SAMPLE SIZE

The sample size/power calculations were performed based on the primary endpoint of change of HbA1c from Baseline to Week 52 in the intent-to-treat (ITT) population. Assuming a common standard deviation (SD) of 1.1%, and the true difference between sotagliflozin 400 mg and glimepiride is zero, 310 patients in the sotagliflozin 400 mg and glimepiride groups will ensure that the upper bound of the 2-sided 95% confidence interval (CI) of the adjusted mean difference is below 0.3% with at least 90% power. This sample size will have 80% power to test the non-inferiority of change of HbA1c from Baseline to Week 52 in completers, with a 30% dropout rate.

A sample size of 310 patients in sotagliflozin 400 mg group and 155 patients in placebo group will have more than 99% power to detect a treatment difference of 0.6% in mean HbA1c change from Baseline to Week 26 between sotagliflozin 400 mg and placebo (SD 1.2%; 2-sided 5% significance level).

A sample size of 155 patients in sotagliflozin 200 mg group and 155 patients in placebo group will have 95% power to detect a treatment difference of 0.5% in mean HbA1c change from Baseline to Week 26 between sotagliflozin 200 mg and placebo (SD 1.2%; 2-sided 5% significance level).

The total sample size is 930 patients to be randomized (sotagliflozin 400 mg group: 310; sotagliflozin 200 mg group: 155; glimepiride: 310; placebo: 155).

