- All serious TEAEs regardless of relationship and related to IMP, by primary SOC, HLGT, HLT, and PT, showing the number (%) of patients with at least one serious TEAE, sorted by the internationally agreed SOC order. The other levels (HLGT, HLT, PT) will be presented in alphabetical order.

Analysis of all treatment-emergent adverse event(s) leading to treatment discontinuation

- All TEAEs leading to treatment discontinuation, by primary SOC, HLGT, HLT, and PT, showing the number (%) of patients sorted by the internationally agreed SOC order. The other levels (HLGT, HLT, PT) will be presented in alphabetical order.

Analyses of adverse events of special interest

Pregnancy and overdose will be included in overall AE summaries if any are reported. ALT increase >3 x ULN is included in laboratory PCSA summary if any.

In addition, the number (%) of patients with an AESI will be summarized by PT and by treatment group. Corresponding listings will be provided as appropriately.

Analyses of events of special interest

CV events, bone fracture and DKA

For EOSIs that are adjudicated (ie, deaths, myocardial infarction, stroke, and unstable angina requiring hospitalization, heart failure requiring hospitalization, bone fractures, and DKA), the number (%) of patients with an EOSI positively adjudicated by CEC will be summarized by treatment group. All EOSIs sent for adjudication and/or reported by the Investigators in the specific AE forms will be listed along with the adjudication outcome.

Renal events

For the EOSI renal events where selected events are adjudicated, the number (%) of patients with any renal events identified in [Table 3](#) in [Section 2.1.4.2](#) will be summarized by treatment group.

The following renal events will be listed along with the adjudication outcome if applicable, including events,

- A) Recorded in e-CRF “GFR decrease”,
- B) Recorded in e-CRF “Renal Event - Dialysis”,
- C) Identified as “Renal transplant” in e-CRF “Other procedure”.

Renal death will be part of all deaths specified above.

Other EOSIs

For EOSIs that are not adjudicated, the number (%) of patients with at least one event will be summarized by treatment group and by PT (as identified in [Table 3](#) in [Section 2.1.4.2](#)).

Severe hypoglycemia will be included in the summary of hypoglycemia (see [Section 2.4.5.1](#)).

Adverse event (AE) leading to an amputation is described in the section below.

Analysis of Amputation

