When a patient has more than one measurement from the central laboratory for the same laboratory parameter on the same date, the average of the measurements will be used. For the same laboratory parameter, if a patient has more than one measurement on different dates for the same scheduled visit, the value closest to the date of the visit will be used for the scheduled visit. When the values for the same scheduled visit are equidistant, the last value should be used for the scheduled visit. Similar rules will be applicable to a patient who has more than one set of measurements for the same vital sign parameter (ie, SBP, DBP, or HR) on the same date.

Time-to-event analysis

For time-to-event analysis/KM plot, time-to-event (eg, treatment discontinuation, rescue therapy, hypoglycemia, etc) is defined as the number of days from the date of the first administration of double-blind IMP (or the date of randomization if not exposed) to the start date of the first occurrence of the event during the 52-week double-blind treatment period.

Patients who did not experience any event during the 52-week double-blind Treatment Period are considered censored observations. For time-to-treatment discontinuation/rescue therapy, censoring date is the date of EOT. For time-to-severe or documented hypoglycemia, censoring date is date of EOT + 1 or date of EOS, whichever is the earliest. Date of EOS will be used if date of EOT is not available. Last contact date will be used if date of EOS is not available.

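### The planned Kaplan-Meier curve for discontinuation due to adverse events treats other-reason stops as censored, so it can only overstate the cumulative incidence it is meant to show

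*SAP*

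**What the plan says.** SAP 2.2 (Disposition of patients) announces "Kaplan-Meier (KM) plots of the cumulative incidence of double-blind IMP discontinuations due to any reason and due to AEs" over the treatment period and refers to SAP 2.5.4 for the rules. Two sentences there matter:

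- Who is censored: "Patients who did not experience any event during the 52-week double-blind Treatment Period are considered censored observations".
- When: "For time-to-treatment discontinuation/rescue therapy, censoring date is the date of EOT".

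No competing-risk estimator is named for these plots.

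The plan also reports the same outcome as crude proportions. In SAP 2.2, "Reasons for treatment discontinuation will be supplied in tables giving numbers and percentages by treatment group", and for these categories "the percentages will be calculated using the number of randomized patients within each treatment group as the denominator". SAP 2.4.5.2 adds "All TEAEs leading to treatment discontinuation, by primary SOC, HLGT, HLT, and PT, showing the number (%) of patients".

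**The concern.** In the AE-specific curve, the event is stopping study drug because of an AE. A patient who stops for another reason has not had that event, so the rule in SAP 2.5.4 makes the patient a censored observation on the stopping date. Kaplan-Meier assumes that a censored patient remains at the same future risk as those still followed. Someone who has permanently stopped the drug cannot later stop it because of an AE, so that assumption fails.

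One minus Kaplan-Meier then estimates how many would stop for AEs if nobody stopped for anything else. That is not the cumulative incidence named in SAP 2.2.

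The report would also disagree with itself. The clock in SAP 2.5.4 starts at randomization for unexposed patients, so the curve can cover the same people as the disposition table. Treatment lasts a fixed 52 weeks, so a correct curve should finish at essentially the tabulated AE percentage. The planned curve would finish above it, with nothing to explain the gap.

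**Working it through.** **Plan's own figure.** The documents state no incidence of AE discontinuation, so there is nothing on this point to reproduce. The only dropout figure is in SAP 1.3: 80% power "in completers, with a 30% dropout rate". That calculation reproduces: 310 × 0.70 = 217 per arm, with SD 1.1% and margin 0.3%, gives 81.1% power.

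**What the 30% covers.** It is a loss rate for the completers analysis. SAP 2.3.1.2 defines completers as patients who finish treatment without starting rescue. Under Protocol 8.2.2, a rescued patient is not a treatment stop: "The patient continues the study treatment (blinded) and stays in the study in order to collect efficacy and safety information". The 30% can therefore include patients who never stop the drug. It serves below only as the upper end of an assumed range.

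**Assumptions.** Constant cause-specific hazards over 52 weeks; total discontinuation T; share s of the stops due to AEs. Neither T nor s is given in the documents.

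**Formulas.**

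- True cumulative incidence (what Aalen-Johansen targets): T × s.
- 1 − KM with other-reason stops censored: the total hazard is −ln(1 − T) and the AE hazard is s times that, so 1 − KM = 1 − (1 − T)^s.
- Upper bound, if all other-reason stops come first: Ts / (1 − T(1 − s)). If all AE stops come first, the excess is zero.

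| T | s | True | 1 − KM | Excess (points) | Relative | Largest possible excess (points) |
|---|---|---|---|---|---|---|
| 10% | 20% | 2.00% | 2.09% | 0.09 | 4.3% | 0.17 |
| 10% | 33% | 3.30% | 3.42% | 0.12 | 3.5% | 0.24 |
| 10% | 50% | 5.00% | 5.13% | 0.13 | 2.6% | 0.26 |
| 30% | 20% | 6.00% | 6.89% | 0.89 | 14.8% | 1.89 |
| 30% | 33% | 9.90% | 11.10% | 1.20 | 12.2% | 2.49 |
| 30% | 50% | 15.00% | 16.33% | 1.33 | 8.9% | 2.65 |

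Worked line: T = 0.30, s = 0.50 gives 1 − 0.70^0.5 = 1 − 0.8367 = 16.33%, against 0.30 × 0.50 = 15.00%.

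**Simulation check.** With 5% AE stops and 25% other stops, the average 1 − KM is 5.8% and the average true proportion 5.0%, at both 310 and 155 patients per arm. The formula gives 5.77%.

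**Between arms.** Hold the true AE incidence at 5% in both arms and vary only the other-reason stops:

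| Other-reason stops | Plotted 1 − KM | Spurious difference (points) |
|---|---|---|
| 10% vs 10% | 5.27% vs 5.27% | 0.00 |
| 10% vs 15% | 5.27% vs 5.43% | 0.15 |
| 10% vs 20% | 5.27% vs 5.59% | 0.32 |
| 5% vs 25% | 5.13% vs 5.77% | 0.64 |

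**The case against.** The strongest reply is that the right number is already planned. The disposition table gives reasons for stopping over all randomized patients, and with fixed 52-week treatment those crude proportions are close to the Week 52 cumulative incidence. This stands, and it keeps the point minor. The tables do not show timing, however, and the curve is the planned display of when patients stop for AEs.

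Second, the effect is small against sampling error. Take a true 8% in two arms of 310, with other-reason stops of 12% and 22%. The curves would read 8.5% and 9.1%, about 0.5 point apart. The standard error of the difference is √(2 × 0.08 × 0.92 / 310) = 2.2 points. The plot carries no test. This also stands.

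Third, the SAP never says in words that other-reason stops are censored in the AE plot. That is true: the handling follows from a general rule whose example event is discontinuation without a cause. But it is the only rule given, and SAP 2.2 points to it.

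Three stronger readings are tempting, and the documents do not support them:

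- **The bias differs by arm.** No rates by arm are given, and the distortion between arms is zero if other-reason stops are equal.
- **The plan expects 30% to stop study drug.** The 30% is a non-completer rate that can include rescued patients still on drug.
- **Dropout for lack of efficacy will distort the tolerability comparison.** Poor control leads to rescue with study drug continued, and lack of efficacy is not among the listed reasons for permanent discontinuation in Protocol 10.3.3. Patients may still stop for any reason, so this route is weakened but not closed.

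**Conclusion.** The point holds as a minor one about a descriptive display. Applied as written, the SAP's rule makes the AE-specific curve estimate something other than the quantity it names, and the error runs in one direction only. Under the assumed totals and shares with constant hazards, the excess is about 0.1 to 1.3 points at Week 52. It ranges from zero to about 2.6 points if the order of AE and other stops is left free. A distortion between arms is possible but not established: about 0.3 point at 10% versus 20% other-reason stops, about 0.6 point at 5% versus 25%, and none if they are equal. No efficacy conclusion or hypothesis test is affected.

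**What to change.** In SAP 2.2 and 2.5.4, specify that the AE-specific curve is an Aalen-Johansen cumulative incidence curve by treatment group, with study drug discontinuation for any other reason as the competing event. Keep Kaplan-Meier for the any-reason curve. Its Week 52 value should then agree, apart from any genuine censoring, with the AE row of the disposition table, which is a useful programming check.

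If the Kaplan-Meier version is kept, label it as 1 − KM with other-reason stops censored, and refer the reader to the disposition table for the incidence.

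The cost is a procedure option or a short macro. The date of stopping and the reason are already collected (Protocol 10.2.1 and 10.3.3), so no new data are needed.
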